#### 1.3.2 Preliminary Clinical Data Using AAV2-Pseudotyped AAV Vectors

A number of clinical trials with an AAV2-based vector delivering the hREP-1 encoding choroideremia gene have been conducted or are currently open in the United Kingdom, Canada, United States, and Germany (www.clinicaltrials.gov NCT01461213, NCT02407678, NCT02077361, NCT02553135, and NCT02671539). The initial results from six enrolled subjects in the United Kingdom receiving  $1 \times 10^{10}$  vg indicated no clinical significant effects from detachment of the fovea and subretinal vector administration and no vector-related toxicity (MacLaren *et al.*, 2014). Two patients who had low baseline best corrected visual acuity showed gain of letters with the treated eyes six months after vector administration and the retinal sensitivity in the treated eyes in all patients was correlated with the vector dose administered per mm^2 of surviving retina. This early improvement was sustained at 3.5 years after vector administration (Edwards *et al.*, 2016). In 2018, a randomized, open label, and parallel controlled phase 3 trial (www.clinicaltrials.gov NCT03496012) was initiated in United States, Canada, Finland, Germany, Netherlands, and United Kingdom.

#### Summary of human studies using AAV2-hRPE65v2

While there is limited reports of clinical trial data of AAV vector mediated gene delivery for choroideremia (MacLaren et al., 2014; Edwards et al., 2016), there are considerable data for RPE65 using AAV2. Two Phase 1 studies were conducted for AAV2-hRPE65v2, a Phase 1 study (101) and a Phase 1 follow-on study (102), involving the same twelve study participants. AAV2-hRPE65v2 was initially tested in a Phase 1, first-in-human, open-label, dose escalation safety study of patients with inherited retinal dystrophy due to autosomal recessive RPE65 gene mutations. The primary objective of the 101 study was to determine the safety and tolerability of gene transfer by subretinal administration of AAV2-hRPE65v2; a secondary objective was to assess both the objective and subjective clinical measures of efficacy in patients with RPE65 gene mutations. Eleven of twelve subjects from the 101 study were transferred to the 102 study to receive the same vector administration to the contralateral eve in the 101 study; one additional subject who participated in the 101 study was not eligible for the . As such, enrollment for the study was closed 102 study in 2013. The primary objective of the 102 study was to assess the safety and tolerability of nonsimultaneous, bilateral subretinal administration of AAV2-hRPE65v2 (administration to the contralateral eye). The secondary objective was to evaluate the efficacy of administration of AAV2-hRPE65v2 to the contralateral eye, using pre-injection measurements of the eye injected as a control. At the time of initiation of the 102 study, all subjects had completed at least their Year One 101 study visit. A Phase 3, randomized controlled (301) study of AAV2-hRPE65v2 enrolled twenty-nine participants with all intervention subjects received non-simultaneous, bilateral administration of AAV2-hRPE65v2. The objectives of the 301 study are to assess the safety, tolerability, and efficacy of sequential, bilateral, subretinal administration of AAV2hRPE65v2 to subjects with RPE65 gene mutations. In addition to monitoring for safety and tolerability, efficacy is evaluated using a number of retinal and visual function tests. After at least one year from the baseline evaluations, nine control participants were able to cross over to receive administration of AAV2-hRPE65v2. There were no serious adverse events related to AAV2-hRPE65v2 and no deleterious immune responses observed in the Phase 3 trial, or in the earlier Phase 1 trials. These trials demonstrated, based on its presumed mechanism of action (recovery of biochemical activity of the RPE65 protein) and the broad range of mutations included in the clinical trials, AAV2-hRPE65v2 is indicated for the improvement of clinical symptoms of vision loss, including nyctalopia, in patients with confirmed biallelic RPE65

mutation-associated retinal dystrophies (Maguire *et al.*, 2008; Maguire *et al.*, 2009; Simonelli *et al.*, 2010; Bennett *et al.*, 2012; Bennett *et al.*, 2016; Russell *et al.*, 2017). AAV2-hRPE65v2 (voretigene neparvovec, trade name: LUXTURNATM) was approved by FDA on December 19, 2017 and European Commission on November 23, 2018 for treatment of inherited retinal dystrophy patients with confirmed biallelic *RPE65* mutations and who have sufficient viable retinal cells.

## 1.4 Non-Clinical Studies of AAV2-hCHM

## 1.4.1 In Vitro Pharmacology of AAV2-hCHM

Due to the lack of an animal model of CHM that mimics the human disease, *in vitro* models of the disease were developed for pharmacology studies (Vasireddy *et al.*, 2013). Two induced pluripotent stem cell (iPSC) lines (CPS1 and CPS2) were generated from two unrelated individuals with confirmed *CHM* gene mutations. The loss of REP-1 protein was confirmed by western blot analysis in both cell lines. A fibroblast cell line was subsequently generated from CPS1 and was named CPF1. These cell lines were used to evaluate the AAV2-hCHM vector for its ability to confer REP-1 activity.

Choroideremia patient-derived induced pluripotent stem cells were then transduced with AAV2-hCHM at MOIs of  $1 \times 10^2$ ,  $1 \times 10^3$ ,  $1 \times 10^4$ ,  $1 \times 10^5$ , or  $2 \times 10^5$  vg/cell. Wild type induced pluripotent stem cells were also plated, but not transduced, and used as a control for normal REP-1 expression levels. Expression of REP-1 was evaluated by flow cytometry using an anti-REP-1 antibody. A qualitative comparison between untransduced wild type cells and CHM cells transduced with AAV2-hCHM at an MOI of 1x10^5 showed similar levels of REP-1 expression. Transduction of all three cell types (CPS1, CPS2 and CPF1) with AAV2-hCHM at an MOI of  $2 \times 10^5$  vg/cell resulted in the expression of REP-1 protein (Vasireddy *et al.*, 2013), which was primarily localized to the cytoplasm. Additional studies were performed to determine if the REP-1 protein encoded by the AAV2-hCHM vector had biological activity. REP-1 plays a key role in the post-translational lipid modification of Rab small GTPases (Rabs), a process called prenylation. In addition, REP-1 is required for escort of prenylated Rab proteins to their target membranes. Thus, to assess the biological activity of REP-1 expressed from AAV2-hCHM, assays were employed to determine if Rab proteins were prenylated and subsequently escorted to the cell membrane. When CPF1, CPS1 and CPS2 cells were transduced with AAV2-hCHM at an MOI of  $2x10^5$ , the REP-1 protein was capable of prenylating its substrate (Rab27) and the amount of Rab27 associated with the cell membrane was similar to that seen in unaffected normal cells (Vasireddy et al., 2013). To screen for shortterm toxicity resulting from transduction with AAV2-hCHM, CHO cells were evaluated for apoptosis by TUNEL staining following infection by AAV2-hCHM at MOIs of  $1 \times 10^5$  or  $2 \times 10^5$ . Neither dose of AAV2-hCHM resulted in cell death in the CHO cells. These studies demonstrate that AAV2-hCHM is capable of safely delivering a biologically active REP-1 protein.

## 1.4.2 In Vivo Pharmacology and Toxicology of AAV2-hCHM

One of the challenges in developing gene therapy for CHM is the lack of animal models that mimic the human disease. Unfortunately, the mouse model that exists for CHM does not reflect the human condition accurately and currently no other small or large animal models with

choroideremia-like disease have been identified. Thus, the safety of delivering AAV2-hCHM to the subretinal space was evaluated in normal wild-type mice and NHPs.

## Safety in Normal Mice

To evaluate the safety of *in vivo* expression of AAV2-hCHM, wild type mice were injected subretinally with the recombinant adeno-associated viral vectors (rAAV) at a dose of 2.7x10^10 vg/retina. Three weeks post-injection, retinal tissues were collected for protein analysis and histologic analyses. Immunoblot analysis of the retinal tissue from these animals confirmed the presence of REP-1 protein of the expected size and immunofluorescence analyses of the retinal sections confirmed the expression and localization of REP-1 protein to the inner segment and outer nuclear layers of photoreceptors and to RPE cells. The number of rows of nuclei in the outer nuclear layer was similar in treated and control mice indicating that there were no short-term degenerative changes in photoreceptors resulting from continuous expression of REP-1. In addition, in mice injected with AAV2-hCHM, retinas obtained 3 weeks after subretinal injection showed no increase in TUNEL positivity, confirming no cell death. There was also no evidence of inflammatory infiltrate in these murine tissues as judged by hematoxylin and eosin staining. Thus, our studies using AAV2-hCHM in mice have demonstrated that after subretinal injection, the *CHM* transgene is expressed in both RPE cells and in photoreceptors and no toxicity was observed (Vasireddy *et al.*, 2013).

In summary, delivery of AAV2-hCHM results in the expression of REP-1 in CHO and patientderived iPS cells *in vitro*, and delivery to retinal cells *in vivo* results in no significant evidence of toxicity. The non-clinical data indicate that the REP-1 expressed from AAV2 in patientderived iPS cells is able to prenylate its substrate and restore significant trafficking of Rab27 protein to the surface of the cell.

## Safety in Non-Human Primates

A toxicology study was designed with assistance of FDA CBER representatives at a pre-IND meeting held March 11, 2013. The study was designed to include twelve (12) male non-human primates (NHP, Macaca fascicularis, Cynomolgus monkeys) for injection of either vehicle or AAV2-hCHM at two different doses and two routes of administration. GMP-process comparable AAV2-hCHM vector or vehicle was injected using the same volume (approximately 300 µL per retina), as well as the same injection device proposed for the clinical study. Each animal was injected bilaterally with either vehicle or vector. The material injected included: (a) Vehicle alone subretinally into each eye of two NHPs; (b) AAV2-hCHM at  $3x10^{11}$  vg subretinally into each eye in four NHPs (a dose which is 6-fold greater than the proposed starting Dose Group 1 for the human CHM trial, and 3-fold greater than that of Dose Group 2 of the human CHM trial; (c) AAV2-hCHM at  $7.5 \times 10^{11}$  vg per retina, into each eye in four NHPs (a dose which is 15-fold greater than the proposed starting Dose Group 1 for the human CHM trial, and 7.5-fold greater than that of Dose Group 2 of the human CHM trial; and (d) AAV2-hCHM at  $7.5 \times 10^{11}$  vg into each eye injected intravitreally in two NHPs, to provide a "worst case scenario' for the complications of injection. Half of the animals in each group were sacrificed at 3 weeks and the other half at 3 months post-injection.

After ocular injections and peri-operative administration of sub-conjunctival triamcinolone and ophthalmic prednisone and gentamicin, animals were followed for in-life observations and

blood tests. Blood tests included complete blood counts (CBCs), serum chemistries, and serum for immunological parameters (humoral and cellular immune responses against AAV2 and antibodies against hREP-1). Tissue histopathology, including ocular histopathology, was performed upon sacrifice.

There were no clinical observations attributed to administration of the test article. There were no definitive test article-related changes in hematology parameters or in serum chemistries. Immunological testing of serum for anti-AAV humoral activity was as expected, showing elevations of anti-AAV2 antibodies in all but one animal receiving AAV2-hCHM; however, no cellular immune responses against AAV2 capsid were detected at any time points evaluated. A possible low-level antibody response directed against REP-1 was observed in one high dose animal, but the data are not conclusive at this time. No test article-related macroscopic or microscopic findings in non-ocular tissues were noted at necropsy on Day 21 or 91 and there were no test article-related changes in organ weights. Thus, no definitive test article-related systemic toxicities were noted following a single subretinal or intravitreal injection of AAV2-hCHM to Cynomolgus monkeys following either a 21-day or 91-day recovery period.

Ophthalmologic evaluations revealed that in the large majority of animals the subretinal injection caused large retinal bullae that resolved over the course of the study leaving focal pigmentary disturbances of the fundus and/or pigment dispersion onto the lens capsules in some animals.

Histopathological examination of the eyes in this study, including those that received vehicle, demonstrated changes in the RPE associated with the location of the subretinal injection site. Inflammation appeared to be a dose and time dependent phenomenon in most cases, but in all eyes that exhibited inflammation, it was graded as no worse than mild. Structural changes in the photoreceptors were only identified in two of four eyes injected with the high dose of vector and sacrificed at Day 91. These changes were mild and focal in nature, not affecting the entirety of the retina.

The investigative team is not certain if the mild focal loss of photoreceptors observed in two of four eyes injected with the high dose of AAV2-hCHM and sacrificed at day 91 was due to complications of the subretinal injection, the AAV2 capsid, or expression of human REP-1 in cynomolgus monkeys. Since similar and higher doses of AAV2-hRPE65v2 did not lead to photoreceptor loss when injected into the eyes of this same species of monkeys, this finding is not likely due to the AAV2 capsid. However, it is possible that it could be due to expression of a foreign transgene, as there are 18 amino acid differences between the human and cynomolgus REP-1 proteins, while there is only a single amino acid difference between the human and cynomolgus hRPE65 proteins. Thus, it is more likely that the hREP-1 protein will be viewed as a foreign antigen than hRPE65.

In the Phase 1/2 clinical trial, reaction to the human REP-1 transgene product is less likely. The investigative team believes the results obtained in the NHP study support the use of two dose levels in the proposed Phase 1/2 clinical trial, namely  $5x10^{10}$  vg/eye and  $1x10^{11}$  vg/eye.

In a separate NHP study, one cynomolgus monkey for each of the dose groups  $(5x10^{11}, 7.5x10^{11}, and 2x10^{12} vg per eye)$  received AAV2-hCHM via bilateral subretinal injections (Couto, 2016 ARVO Meeting; Ignatova, 2016 ASGCT Meeting). Retinal tissues from the

vector exposed area (bleb), as well as from outside the bleb area, were harvested 30 days after the injection. Retina tissues from three uninjected NHPs were used as control in a speciesspecific quantitative Reverse Transcription Polymerase Chain Reaction (RT-PCR) assay. Human REP-1 expression was observed at robust levels within the bleb area and at very low levels outside the bleb area. Furthermore, analysis on the ratios of human REP-1 expression level to endogenous cynomolgus REP-1 expression level suggests that the two doses in this study,  $5x10^{10}$  vg/eye and  $1x10^{11}$  vg/eye, are likely to provide supraphysiologic levels of human REP-1 protein in the vector exposed area of retina.

#### 1.5 Selection of Drugs and Dosages

The investigational product is

AAV2-hCHM is an AAV serotype 2 vector containing the normal human *CHM* gene encoding REP-1 (Rab escort protein-1) under the regulatory control of the hybrid chicken  $\beta$ -actin promoter coupled to the human cytomegalovirus (CMV) enhancer. Doses to be administered for the proposed inter-subject group dose escalation study design include Dose 1 of up to  $5 \times 10^{10}$  vg per eye and Dose 2 of up to  $1 \times 10^{11}$  vg per eye. Dose selection is based on previous *in vitro*, *in vivo* and clinical data from initial Phase 1, Phase 1 follow-on, and Phase 3 studies of the RPE65 gene therapy trial (FDA IND #13408) and from the *in vitro* and *in vivo* data for AAV2-hCHM (Sections 1.4.1 and 1.4.2), demonstrating that AAV2-hCHM-mediated delivery of REP-1 to patient-derived iPS cells is able to normalize prenylation and restore trafficking of Rab27 protein to the surface of the cell. The results of the NHP study also help guide the dose selection for this clinical trial (see summary in Section 1.4, above).

#### 2 STUDY OBJECTIVES

#### 2.1 Primary Objectives

The primary objectives are to evaluate the safety and tolerability of subretinal administration, in an inter-subject group dose escalation, of AAV2-hCHM in adults with choroideremia.

#### 2.2 Secondary Objectives

The secondary objectives are:

a) To define the dose of AAV2-hCHM required to achieve stable, or improved visual function and functional vision in subjects with choroideremia; and

b) To characterize the immune responses to the *CHM* transgene protein product (REP-1) and AAV2 capsid proteins following subretinal administration of AAV2-hCHM.

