potential eligibility, gene therapy informed consent is conducted prior to the extensive Baseline evaluation. The Baseline evaluation will be comprised of medical history and comprehensive visual and laboratory assessments (including confirmation of genetic diagnosis if adequate records are not available). If all of the criteria indicate study eligibility, the subject is offered the opportunity of vector administration and participation in the active phase of the study.
Study Intervention (Vector Administration) : After confirmation of eligibility and subject agrees to study entry, the investigational product (AAV2-hCHM) is administered in the operating room on Day 0 via unilateral subretinal injection under general anesthesia to the subject's non-preferred eye (or the eye with worse visual acuity if the subject has no preference). The subject is maintained for up to 24 hours in a supine position following the procedure. The subject may be discharged during this 24-hour time period, if stable, provided the post-operative supine positioning can be maintained.
Active Phase Follow-Up: Analyses will include safety endpoints such as adverse events, comprehensive blood and urine laboratory tests, vector presence in blood and tears, pregnancy outcomes (in female partners of subjects), as well as ophthalmologic safety and efficacy endpoints including ophthalmic examination, and measures of visual function, functional vision, ophthalmologic imaging, and quality of life (QOL) questionnaire. The schedule of evaluations in the active phase will be conducted over an approximately 2-year period post vector administration to assess safety and efficacy of AAV2-hCHM (including the administration), comparing the findings obtained longitudinally from the injected eye with those of the uninjected eye serving as the control.

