#### 1.1.3 Choroideremia as a Model for Gene Therapy

Retinal degenerative diseases such as choroideremia are rational targets for gene therapy using AAV. First of all, the use of an AAV2 pseudotyped vector has shown safety and utility in both animal models and human subjects with autosomal-recessive RPE65 gene mutations (Acland et al., 2001; Acland et al., 2005; Maguire et al., 2008; Bainbridge et al., 2008; Hauswirth et al., 2008; Maguire et al., 2009; Amado et al., 2010; Mingozzi and High, 2011; Bennett et al., 2012; Jacobson et al., 2012; Cideciyan et al., 2013) providing impetus to develop research programs for other retinal degenerative diseases that have no currently effective treatment. Since the degenerative changes of choroideremia generally progress slowly over time, the results of unilateral vector administration can be assessed and verified, when compared to the uninjected control eye. The subretinal space has been shown to provide a favorable environment for AAV to deliver a normal gene to the RPE layer (Bennett et al., 1999; Acland et al., 2001; Jacobson et al., 2006b; Maguire et al., 2008; Bainbridge et al., 2008; Hauswirth et al., 2008; Maguire et al., 2009; Amado et al., 2010), and the limited size of the target allows for efficient transduction of retinal cells. Both *in vitro* and *in vivo* results demonstrate that the REP-1 protein is translated at levels potentially sufficient to result in a clinically relevant change within the eye (see sections 1.4.1 and 1.4.2, below). Importantly, since high levels of the transgene protein do not appear to be toxic (Tolmachova et al., 2012), over-expression of REP-1 protein that may potentially occur in the context of gene therapy is not predicted to be harmful. Finally, since the eye is immune-protected, the relative lack of an immune response against the capsid protein of AAV2 and against the transgene protein may provide the ideal milieu for advantageous long-term transgene expression.

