As is always the case with subretinal injection, the operating surgeon has latitude in administration of the dose, based on the pathophysiology of the subject's retina. In choroideremia in particular, it is anticipated that some patients will have limited access for injection due to degenerative disease. For this reason, all doses are specified as "up to 300  $\mu$ L," recognizing that some subjects may receive a smaller total subretinal volume than 300  $\mu$ L, and as such, may not receive the total dose. This information will be captured should this occur.

Following unilateral vector administration under general anesthesia, the subjects will be followed up comprehensively for safety and efficacy endpoints for two years after injection, then up to an additional 3 years (total of up to 5 years) of long-term follow-up. Based on the pathophysiology of choroideremia, the investigative team does not anticipate the nearly immediate improvement of light sensitivity, to the extent that resulted for the RPE65 gene therapy studies (Maguire *et al.*, 2008; Maguire *et al.*, 2009; Bennett *et al.*, 2012). Additionally, the visual deterioration of choroideremia generally progresses more slowly than that associated with autosomal-recessive *RPE65* gene mutations (Rosenberg & Schwartz, 1994; Roberts *et al.*, 2002). The slower decline of visual function of choroideremia means that the use of the uninjected eye as a control for the injected eye becomes more statistically significant as sufficient time lapses between injections. Therefore, to minimize risk to subjects, administration of investigational product will be done in one eye for this study.

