#### Plans for Follow-On Study

If the vector product is tolerated and effective in the two dosage groups over the follow-up period, the DSMB will discuss the possibility of a separate follow-on study for a second eye injection of the previously uninjected, contralateral eye.

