### 2.1.2 Secondary Objectives

The secondary objectives of this study are:

- To define the dose of AAV2-hCHM required to achieve stable, or improved visual function and functional vision in subjects with choroideremia.
- To characterize the immune responses to the *CHM* transgene protein product (REP-1) and AAV2 capsid proteins following subretinal administration of AAV2-hCHM.

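### Secondary objective (a) accepts stable function without reference to the uninjected eye, so in a slowly progressive disease an inactive dose could meet it

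*Protocol*

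**What the plan says.** Protocol 2.2 gives secondary objective (a) as "To define the dose of AAV2-hCHM required to achieve stable, or improved visual function and functional vision in subjects with choroideremia". SAP 2.1.2 repeats it ("To define the dose of AAV2-hCHM required to achieve stable, or improved visual function", continuing as in the protocol). Neither document says which measure, loss, time point or share of subjects makes function stable.

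On natural history, Protocol 1.1.3 reasons from slow progression ("Since the degenerative changes of choroideremia generally progress slowly over time"). Protocol 3.1 adds that "the visual deterioration of choroideremia generally progresses more slowly than that associated with autosomal-recessive" RPE65 disease, and that the rapid gains seen in the RPE65 studies are not expected here. Protocol 4.2 says the two eyes of a patient generally behave alike.

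On the control, the Protocol Synopsis (Active Phase Follow-Up) describes assessment by "comparing the findings obtained longitudinally from the injected eye with those of the uninjected eye serving as the control". Protocol 3.1 says that "the use of the uninjected eye as a control for the injected eye becomes more statistically significant as sufficient time lapses". Exclusion criterion 7 removes grossly asymmetric disease to protect that control.

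On analysis, SAP 4 states no hypotheses about treatment effects and promises descriptive summaries by dose cohort. SAP 4.6 plans no derivations. SAP 6 calls all efficacy analyses exploratory. SAP 6.1 specifies listings by injected and control eye. Only SAP 6.1.6 (microperimetry) says the eyes will be compared, and it gives no method.

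On use of the result, the follow-on paragraph of Protocol 3.1 opens "If the vector product is tolerated and effective in the two dosage groups over the follow-up period" and then provides for the DSMB to discuss a separate study injecting the second eye.

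**The concern.** An objective that stability alone can satisfy needs a reference for what would have happened without the vector. Where decline is slow, an untreated eye may also look stable over the two-year active phase. Because the eyes generally run in parallel, an inactive dose would tend to leave both about where they started. The injected-minus-uninjected difference is then near zero, yet the objective as worded is met.

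At stake is what the trial can later claim about dose. The margin is undefined and the study is open label, so stabilisation could be claimed for a cohort after the data are seen, without the fellow eye entering the claim. Protocol 6 makes an indication of efficacy, together with a favourable safety profile, the condition for proposing follow-on studies. The second-eye paragraph relies on the word effective. Neither term is defined.

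**Working it through.** The plan has no figure to reproduce: it states no decline rate, SD, stability margin, hypothesis or power. The calculation below is an illustration on assumed inputs, for acuity only.

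**Inputs from the documents.** Cohorts of 5 and 10 (SAP 3.1); active phase of 2 years, follow-up to 5 years (Protocol 3.1). The only letter threshold is the 15-letter asymmetry limit in exclusion 7. It is not a stability margin and serves only as the top of the range.

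**Assumed inputs.** Decline r = 0.5 to 3 letters per year; SD s of the two-year change = 4 to 8 letters; stable or improved means a change better than −m letters, with m = 0, 5, 10 or 15.

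**Step 1, one eye, no treatment effect.** With change ~ Normal(−2r, s), P(stable or improved) = Φ((m − 2r)/s).

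| m (letters) | r = 0.5 to 2 | r = 3 |
|---|---|---|
| 0 | 0.16 to 0.45 | 0.07 to 0.23 |
| 5 | 0.55 to 0.84 | 0.40 to 0.45 |
| 10 | 0.77 to 0.99 | 0.69 to 0.84 |
| 15 | 0.92 to >0.99 | 0.87 to 0.99 |

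The probability exceeds one half exactly when the two-year decline 2r is smaller than m.

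**Step 2, can stability separate active from inactive?** Take r = 1, s = 5, m = 10. Inactive: Φ((10 − 2)/5) = Φ(1.6) = 0.945. Decline fully halted: Φ(10/5) = Φ(2) = 0.977. Expected stable subjects out of 10 are 9.45 and 9.77.

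**Step 3, cohort level, inactive dose.** Binomial probability that a majority is stable:

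| Per-eye probability | At least 3 of 5 | At least 6 of 10 |
|---|---|---|
| 0.945 | 0.998 | >0.999 |
| 0.80 | 0.94 | 0.97 |
| 0.55 | 0.59 | 0.50 |

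**Step 4, the fellow eye as reference.** With no effect, the difference in change is Normal(0, s√(2(1 − ρ))), where ρ is the between-eye correlation. For s = 4 to 8 and ρ = 0 to 0.5, the injected eye beats its fellow by more than m in 11 to 33% of subjects (m = 5), 1 to 19% (m = 10) and 0 to 9% (m = 15).

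**Step 5, precision of the paired contrast.** With ρ = 0.5 the SD of the difference equals s. The 95% half-width for a cohort mean is t × s/√n:

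- n = 5: 2.776 × 4/√5 = 5.0 to 2.776 × 8/√5 = 9.9 letters.
- n = 10: 2.262 × 4/√10 = 2.9 to 2.262 × 8/√10 = 5.7 letters.

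The difference from fully halting decline at 1 letter per year is 2 letters at Year 2 and 5 at Year 5. As a gauge only, since the plan has no test, two-sided 5% power with n = 10 is Φ(2/(s/√10) − 1.96) = 12 to 35% at Year 2. Replacing 2 by 5, with the same SD, gives 51 to 98% at Year 5.

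**The case against.** The strongest reply is that the comparator is already in the design. The protocol raises slow decline itself and answers it with the uninjected eye, the asymmetry exclusion and follow-up to five years. This stands as a statement of intent, and objective (a) should be read in its light. It does not close the gap: neither the objective nor the SAP says that stability is judged against the fellow eye, and SAP 6.1 gives no paired summary.

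A second reply is that efficacy is exploratory and that no dose is declared effective by any rule. That is right. A reader might infer that the plan contains a decision rule that an inactive dose would trigger, or that would name Dose Group 1. The documents do not support this: objective (a) states an aim, the SAP has no responder definition, and Protocol 6 leaves fuller evaluation of significance to later studies. Nor does the follow-on paragraph equate effective with stable; it leaves the word open.

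Third, the illustration models acuity alone. Protocol 1.1.1 says peripheral vision is affected before central vision, so visual fields may decline sooner than acuity. The Protocol 9.4.2 risk list includes reduced acuity after the procedure, which would lower the stable rate. Requiring stability on several measures together would lower it further: at 0.9 each, with independence, 0.9⁵ = 0.59 for five and 0.9¹⁰ = 0.35 for ten. These points limit the size but do not supply the missing reference.

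**Conclusion.** The concern holds as a gap in wording and analysis. Objective (a) can be met by a stable injected eye whatever the uninjected eye does, and only the unspecified microperimetry comparison carries the fellow-eye control into SAP 6.1. An inactive dose could therefore meet the objective. Under many plausible margins it would do so in a majority of subjects, but that depends on an assumed decline rate, SD and margin for acuity.

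A reader might go further and conclude that an inactive dose meets the objective in most subjects. The documents do not support that as fact: they say slow but give no rate, and the result reverses with a zero margin or when two-year decline exceeds the margin. The amendment is inexpensive and should be made. It does not affect the primary safety objective.

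**What to change.** 1. In the Protocol Synopsis, Protocol 2.2 and SAP 2.1.2, word objective (a) as function that is stable or improved relative to the uninjected eye over the same interval.
2. In SAP 6.1, and in 4.6 as a derivation, summarise by dose cohort the within-subject injected-minus-uninjected difference in change from baseline, with an interval. Do this for each quantitative test measured eye by eye, at Year 2 and at the long-term visits where that test is scheduled. The QOL score has no fellow-eye counterpart, so say so.
3. State that stability of both eyes is not evidence of stabilisation by the vector, and that effective in the follow-on paragraph is read the same way.
4. A within-subject 2×2 table (worsened or not, by eye) may be added as a display only, with the margin for each measure fixed in advance. It should not be the sole basis for judging a dose. In the Step 2 inactive case with independent eyes, 2 × 0.055 × 0.945 = 10% of subjects are discordant, about 0.5 of 5 and 1 of 10. The chance of none in Dose Group 1 is (1 − 0.104)⁵ = 58%.

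The cost is wording and one set of descriptive tables from data already collected. Fewer subjects could be claimed as stabilised, and with 5 and 10 subjects the paired contrast will be imprecise at Year 2. That is why the long-term visits belong in the summary.
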